Cover Page:

The Effects of Dexamethasone on the Time to Pain Resolution in Dental Periapical Abscess

NCT03005522

Document. Date: 12/01/2020

Study Protocol

MATERIALS AND METHODS

A prospective, randomized, double-blind placebocontrolled study was undertaken at two academic medical center EDs between September 2017 and May 2019. All patients presenting with "dental pain" were screened for potential study enrollment. Patients 18 years and older with a clinical diagnosis of pulpitis or dental apical abscess were further screened for potential enrollment. Diagnosis was made based on physical examination revealing pain with percussion of the affected tooth or teeth with or without gingival erythema or swelling.

Patients were excluded for any of the following conditions: diabetes, treatment with systemic corticosteroids within the last 30 days, hospitalization due to intractable vomiting or pain, self-reported pregnancy, immunosuppression (diagnosed with human immunodeficiency virus, received transplantation, or receiving chemotherapy), or those who lacked a telephone number to participate in follow-up calls. Eligible patients were approached for potential study inclusion and, after providing informed consent, enrolled patients were randomized to receive either dexamethasone 10 mg or an identical placebo.

Study drug, placebo, and two separate randomization lists were prepared for each study site by the investigational drug pharmacist. Randomization was achieved by using a random number generator of blocks of four to maintain relatively equal group sizes. The study drug was prepared using capsules filled with either sucralose granules or crushed dexamethasone tablets. Four 2.5-mg tablets were crushed and mixed with sucralose granules for each active study drug preparation. Study drug and placebo were prepared using identical capsules to maintain blinding. The investigators, patients, and treating provider remained blinded. Only the investigational drug pharmacist, who was not involved in the care of these patients, had the ability to unblind the study if necessary for patient safety.

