Medical management of each patient was performed at the discretion of the treating provider. Data on therapeutic modalities, including the use of local anesthetic blocks, analgesics, and antibiotics, were gathered for each patient to allow for comparison between the dexamethasone and placebo groups. Termination from study enrollment occurred if the patient required dental extraction or pulpectomy during the 72-h follow-up period.

Baseline pain scores were obtained after physical examination using the 0-10 Numeric Pain Rating Scale (NPRS). Patient demographic characteristics were also collected at this time. A second pain score and data on treatment regimens used in the ED and any new outpatient prescriptions were obtained at time of discharge. Follow-up pain scores were then obtained at 12-, 24-, 48-, and 72-h intervals thereafter. For follow-up pain scores, telephone calls were made by study coordinators as close as possible to 12, 24, 48, and 72 h after discharge. If the follow-up phone calls were made beyond the 12-, 24-, 48-, and 72-h timeframe, patients were requested to recall their pain scores at the approximate time. During these calls, information was collected about further medical or dental care, analgesic use, and the occurrence of adverse effects. All patients were offered to have a \$10 gift card sent to their home at time of the completion of

Statistical Anaysis

We considered a 2-point difference in the 11-point NPRS to be clinically meaningful (19). Assuming a standard deviation (SD) of 3, power of 80%, and two-sided alpha of .05, we estimated a sample size of 37 patients per treatment group would be necessary to detect this difference. Statistical analysis was performed using Stata software, version 16.0 (College Station, TX). A two-tailed alpha of .05 was used as the threshold of significance for all statistical testing. Chi-square testing was performed for continuous, parametric data and Wilcoxon-rank sum testing was used for categorical and nonparametric data.

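### The plan's only test rule gives chi-square to continuous data and rank-sum to categorical data, and lists no comparison of means although the sample size rests on one

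*Combined protocol and SAP*

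**What the plan says.** The trial is sized in the Statistical Analysis section on the 0-10 Numeric Pain Rating Scale (NPRS): "We considered a 2-point difference in the 11-point NPRS to be clinically meaningful". The inputs are given as "Assuming a standard deviation (SD) of 3, power of 80%, and two-sided alpha of .05", and the result is that "we estimated a sample size of 37 patients per treatment group would be necessary to detect this difference".

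The same section then sets one significance level for everything, "A two-tailed alpha of .05 was used as the threshold of significance for all statistical testing", and closes with the only sentence in the document that names a test: "Chi-square testing was performed for continuous, parametric data and Wilcoxon-rank sum testing was used for categorical and nonparametric data".

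The data to be tested are described under Materials and Methods. Pain is scored at baseline and at discharge, and then "Follow-up pain scores were then obtained at 12-, 24-, 48-, and 72-h intervals thereafter". Use of local anesthetic blocks, analgesics and antibiotics is recorded so that the two groups can be compared. Nothing says whether NPRS scores count as parametric or nonparametric, and no t-test, analysis of variance or regression is mentioned.

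**The concern.** A chi-square test on a 0-10 score treats the eleven values as unordered labels. It asks whether the two groups have the same distribution over those labels. It ignores that 7 is worse than 3, and it does not estimate or test a difference in means.

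The rank-sum test has the opposite problem with nominal data. It needs an order, and for a variable such as type of antibiotic (if coded as one variable with several levels) the only order available is the arbitrary numbering in the data file.

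There is also a mismatch with the sample size. A difference in points divided by an SD is the input to a comparison of two means, and no such comparison is listed. Three things are at stake: whether the pain comparison has the power the plan claims, whether p-values for multi-level nominal variables mean anything, and whether the test for the main outcome was fixed before the results were seen.

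**Working it through.** **1. Reproducing the plan's sample size.** Inputs, all from the Statistical Analysis section: difference 2, SD 3, power 80%, "two-sided alpha of .05". Equal allocation follows from the blocks of four described under Materials and Methods.

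- Normal approximation: n per group = 2 × (1.960 + 0.842)² × 3² / 2² = 35.3, so 36.
- Two-sample t-test (noncentral t, standardised difference 2/3): n = 36.3, so 37. Power is 80.8% at 37 and 79.7% at 36.
- A one-sided test would need 28, which does not match.

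The stated 37 is therefore the t-test figure. The plan does not name that test. It is inferred from the form of the inputs and the exact match.

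**2. Power of each candidate test on 0-10 scores at 37 per group.** The plan gives no group means, so these are assumptions. Normal scores were simulated, rounded, and limited to 0-10. Chi-square was run on the table of two groups by the score values.

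| Assumed means and SD before rounding | t-test | rank-sum | chi-square |
|---|---|---|---|
| 4 and 6, SD 3 (10,000 runs) | 80% | 79% | 33% |
| 3.8 and 6.2, SD 3.6 (2,000 runs) | 79% | 79% | 35% |
| 3.8 and 6.2, SD 3.6 (4,000 runs, separate check) | 78% | 78% | 35% |

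The wider setting in rows two and three was chosen so that, after rounding and limiting, the observed difference (about 1.97 to 1.99) and SD (about 3.02) match the plan's 2 and 3. In that setting about 83% of expected cell counts are below 5, so the chi-square approximation is also poor. Five other placements of the means, with difference 2 and SD 3 before rounding, gave chi-square power of 31-34%. The low figure does not depend on the chosen means.

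**3. Cost of using rank-sum on the scores instead.** For normal data its efficiency relative to the t-test is 3/π = 0.955.

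- Sample size needed: 36.3 / 0.955 = 38.02, so 39 per group. Power at 37 is about 79%.
- At the worst-case efficiency of 0.864: 36.3 / 0.864 = 42.02, so 43 per group. Power at 37 is about 75%.

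**4. Rank-sum on a nominal variable.** Take a hypothetical three-category variable with counts 20/10/7 in one group and 10/20/7 in the other.

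- Categories numbered 1, 2, 3: rank-sum p = 0.08.
- Same data numbered 1, 3, 2: rank-sum p = 0.01.
- Chi-square, any numbering: expected counts are 15/15/7 in each group, so the statistic is 4 × 5²/15 = 6.67 on 2 degrees of freedom, p = 0.036.

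Renumbering alone moves the rank-sum result across the .05 threshold. For a yes/no variable the two tests nearly agree.

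**The case against.** The strongest reply is that the sentence is a drafting slip and that no one would run chi-square on raw pain scores. The NPRS is a bounded integer scale, so it fits naturally in the nonparametric half of the rule, where rank-sum is a valid choice and costs only one or two points of power. Rank-sum is also acceptable for ordered categories. Use of blocks, analgesics and antibiotics can be coded yes/no, where rank-sum and chi-square nearly agree. The document does not show that any score was tested by chi-square, or that any nominal variable had more than two levels.

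Much of this stands as a limit on the consequences. The 33-35% power applies only if the scores are put in the continuous, parametric branch. The coding problem applies only to nominal variables with three or more levels. The sample size of 37 is not wrong.

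It does not rescue the text. The sentence is complete, and nothing elsewhere corrects it. Swapping the two test names would give rank-sum for parametric data and chi-square for nonparametric data, and would still list no comparison of means, so the intended plan cannot be recovered by reading around a slip. The mean-and-SD sizing points to the continuous, parametric branch, which is the one assigned chi-square. Leaving the branch open also lets the test be chosen after the results are known.

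**Conclusion.** The concern holds. The only test rule in the plan is wrong as written for continuous, parametric data and for nominal data with more than two levels. It is right for nonparametric data. The test that the sample size implies, a two-sample comparison of means, is not listed, and no test is assigned to the NPRS scores.

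For the pain scores the consequence runs from a loss of one or two percentage points of power (rank-sum on roughly normal scores) to a fall to about 33-35%, less than half the planned 80% (chi-square on the score values). These figures assume 37 analysed per group, a true difference of about 2 and an SD of about 3. The group means are assumed, and the chi-square figure barely changes with them.

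**What to change.** Replace the sentence with an assignment by data type:

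- Continuous NPRS outcomes: difference in means with a 95% confidence interval, by two-sample t-test or a baseline-adjusted linear model. State which.
- Ordinal or clearly non-normal continuous data: Wilcoxon rank-sum.
- Categorical data (treatments used, adverse effects, further care): chi-square, or Fisher's exact test where expected counts are below 5.

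Name the single test used for the primary pain comparison so that it matches the basis of the sample size. If rank-sum is preferred, say so and state the power at 37 per group as about 79%.

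The section is written in the past tense and enrollment ran from September 2017 to May 2019. The sponsor should therefore also confirm which test was applied to each variable and repeat any comparison that was done as written. The cost is a wording change and a re-run of standard commands. The sample size is unchanged and no new data are needed.
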